C.13. INTERVENTION FIDELITY MONITORING & EVALUATION. The PM will monitor the Facebook group daily to record task-completion rates and caregivers' site visits, respond to caregivers' questions and postings, and review records and posted content to ensure proper posting and functionality. Extension health educators will record caregiver meeting attendance and activities, as well as each preschooler's attendance, punctuality, participation, and activities offered for the day in a daily activity log. The PI will communicate with Extension health educators weekly to review objectives, attendance, and intervention delivery dose, and discuss issues and solutions. Head Start teachers will complete an evaluation survey on preschooler program, and caregivers will complete an evaluation survey on caregiver program and preschooler letters (**Appendix A**). Two process evaluators will observe 6 randomly sampled sessions (2/center; 1 session from Extension health educator and 1 session from teacher) to evaluate preschooler curriculum implementation and activity engagement. At post-intervention, individual interviews (**Appendix A**) with 10 randomly selected caregivers will be conducted with the PM and PI to obtain in-depth evaluation of the intervention and future suggestions for improvement.

C.14. DATA COLLECTION & OUTCOME MEASURES (Table 5, Appendix A). All outcomes will be assessed at baseline and post-intervention. Height and weight will be measured in a private room in Head Start centers. To improve compliance with wearing accelerometers, an auto text-message reminder will be sent to caregivers every morning at 7AM via the *REDCap* web application maintained by MSU CTSI-BRIC (**Support Letter**). The 24-hour dietary recall will be administered by 4 trained interviewers via telephone¹⁴⁰ on 2 weekdays and 1 weekend day,^{141,142} using the Nutrition Data System for Research (NDSR) software developed by the Nutrition Coordinating Center,¹⁴³ University of Minnesota. Trained interviewers will also observe the snacks and lunch offered at Head Start centers. Drs. [name] & [name], who have completed the 2-day training on NDSR, will assess and assure diet data quality. The Environment and Policy Evaluation and Observation-Self-Report (EPAO-SR)¹⁴⁴ will be completed by each center supervisor and two teachers on a single day to assess each

Head Start center environment, including the physical environment, provisions, practices, policies, training, and education. All other surveys will be completed by caregivers online via REDCap web application. Caregivers will be informed of online surveys via text-message or email. Data collectors and interviewers (blinded to group assignment) will be available by phone or in-person to answer questions.

Table 5. Study Measures

Concept	Measure and Description	# Items	Time	Reliability/Validity
Preschoolers (Aim 1)				
MVPA (min/day)	7-day ActiGraph GT3X-plus accelerometer ¹⁴⁵ Cut-points: sedentary activity (<37 counts/15 s), light (38–419), moderate (420–841), & vigorous (≥842) ^{146,147}	7-day	5 min	Reliability = 0.69–0.84 ¹⁴⁸ $r = 0.66$ with observational system ¹⁴⁵
Diet quality (e.g., fruit/vegetable, fiber, sugar/fat)	Intake at Head Start center: dietary observation system on snacks and lunch on two weekdays ¹⁴⁹ Intake at home: proxy-reported 24-hour dietary recall	3-day	90 min	ICC = 0.99; ¹⁴⁹ accurate rate: 95%; ¹⁵⁰ good agreement with actual energy intake ¹⁵¹
Screen Time	NHANES-Physical Activity and Physical Fitness survey ¹⁵²	2	1 min	Reliability: $r = 0.63–0.84$ ¹⁵³
Proportion of OW/O, BMI z-score	Calculated from height and weight using CDC growth charts ¹⁵⁴ Height: Child/Adult Shorr Measuring Board Stadiometer Weight: Child/Adult Seca model 874 portable electronic scale In accordance with NHANES measurement protocol ¹⁵⁵	N/A	3 min	Specificity 0.93; sensitivity 0.73 ¹⁵⁶
Caregivers (Aim 2)				
MVPA	7-day ActiGraph GT3X-plus accelerometer Cut-points: light (0–2689 counts/60 s), moderate (2690–6166), & vigorous (≥6167) ¹⁵⁷	7-day	5 min	ICC = 0.97–0.99 ¹⁵⁸ $r = 0.81$ with oxygen consumption ¹⁵⁹
Diet quality	Fruit-vegetable-fiber screener ¹⁶⁰	10	3 min	$r = 0.71$ with full Block survey ¹⁶⁰
Screen Time	NHANES-Physical Activity and Physical Fitness survey ¹⁵²	2	1 min	Reliability: $r = 0.63–0.84$ ¹⁵³
Proportion of OW/O, BMI	Calculated using (weight kg/height m^2) ¹⁶¹ Measures are similar to those used in preschoolers	N/A	3 min	Specificity 0.97; sensitivity 0.42 ¹⁶²
Knowledge	Knowledge on preschoolers' dietary intake & physical activity ¹⁶³	25	5 min	N/A
Feeding Practice Skill	Child Feeding Questionnaire ¹⁶⁴ measuring caregiver feeding practice behaviors	33	5 min	$\alpha = 0.71–0.93$ ^{38,164,165} $r = -0.26–0.53$ with child BMI ^{164–166}
Self-Efficacy	Parental self-efficacy scale ¹⁶³	20	4 min	$\alpha = 0.72–0.94$ ^{38,163}
Parental Support	Parental support scale for eating habits and physical activity ¹⁶⁷	12	3 min	$\alpha = 0.83–0.87$ ^{38,167,168}
Parenting Practices	Parenting Style and Dimensions Questionnaire ¹⁶⁹ assessing parenting styles: authoritative, authoritarian, and permissive	32	5 min	$\alpha = 0.64–0.91$ ¹⁷⁰
Home Environment	Family Nutrition and Physical Activity (FNPA) screening tool ¹⁷¹ assessing home obesogenic environments and practices	20	4 min	Correlated with child BMI ^{171,172}
Demographics	Socio-demographic questionnaire (e.g., age, sex, race)	12	3 min	N/A
Center Environment	EPAO-SR ¹⁴⁴	1-day	30 min	Related to observational data ¹⁴⁴

C.15. DATA ANALYSIS. Any missing at random (MAR) data will be imputed using procedures suggested by Potthoff.¹⁷³ For non-MAR data, a sensitivity analysis will be performed following recommended approaches for continuous and discrete outcomes.^{174–177} All analyses will use the intention-to-treat¹⁷⁸ principle. Data analysis will be disaggregated by sex in preschoolers. **AIM 1 & 2:** Mixed-effect models in SAS 9.4 will be used to evaluate the intervention efficacy. Fixed effect predictors will include group, time, groupXtime interaction, and potential confounders such as preschooler sex, race, baseline weight status, and caregiver marital status. The correlation of preschooler outcomes measured over time and dependence due to nesting in the same center or class will be accounted through center- and class-specific random cluster effect. Contrasts will quantify the intervention effects separately at the post-intervention. Holm's method will be used to statistically control for multiple comparisons.¹⁷⁹ Effect size (Cohen's d) will be calculated. **AIM 3:** Path analysis will be conducted using EQS 6.2. Model fit will be assessed using root mean square error approximation, Normed Fit Index, and Tucker Lewis index. Chi-square difference test¹⁸⁰ will be used to compare models. Model modification will be made if needed. Feasibility/acceptability/satisfaction will be determined through enrollment, intervention participation, and evaluation survey data. Recorded individual interviews will be analyzed using directed content analysis in ATLAS.ti 8 to evaluate reasons for satisfaction and suggestions for improvement.

Table 6. Method Considerations

Issue	Justification and Strategies
Different participation by Head Start teachers may influence intervention delivery.	• Based on our prior 10-wk study, all six teachers in the intervention classes independently and successfully delivered the last 4 wks. of the program.
Compliance with wearing ActiGraphs.	• We will send daily auto reminders. We will replace broken or misplaced ActiGraphs. Imputation techniques will be used for missing data.
Difficulty meeting recruitment goals.	• We will use Head Start family advocates to help with recruitment. Another center or class will be randomly selected if selected center or class elects not to participate.

Table 7. Timeline for Activities

Months	YEAR 1			YEAR 2		
	1-4	5-10	11-12	1-2	3-6	7-12
IRB approval; hire/train staff; prep materials; purchase supplies.	X	X				
Recruit; enroll; baseline data collection.		X				
16-week "FirstStep2Health" intergenerational intervention.		X	X	X	X	
Immediate post-intervention data collection.				X	X	
Data entry, cleaning, and analysis; presentations and manuscripts.		X	X	X	X	X

REFERENCES

3. Klemetson A, [name] J. A description of food accessibility among urban head start families. The 19th Annual University Undergraduate Research and Arts Forum; 2017; Michigan State University. https://urca.msu.edu/files/forums/28/booklet/2017%20UURAF%20Program%20Book_Digital.pdf
4. [name] JY, [name] LB, Hines-Martin V. Perceived parental barriers to and strategies for supporting physical activity and healthy eating among Head Start children. *J Commun Health*. 2016;41(3):593-602.

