Our **primary objective** is to determine the preliminary efficacy of the intervention. **Methods:** We will conduct a **two-group cluster randomized controlled trial** (RCT). From the available 13 large Head Start centers, six centers will be randomly selected and then randomly assigned to the intervention (n=3) or control group (n=3, usual Head Start activities); 24 caregiver-preschooler dyads will be recruited from each center (N=144 dyads).

AIM 1: Determine the preliminary efficacy of *FirstStep2Health* vs control among preschoolers on proximal behavioral changes of ↑ moderate-to-vigorous PA (MVPA) measured by accelerometry (primary outcome), ↑ diet quality (e.g., ↑ fruits/vegetables, ↑ fiber, ↑ whole grains, ↑ total protein, ↑ dairy, ↓ sugar-sweetened beverages, ↓ total sugars/fats), and ↓ screen time (e.g., watching TV, playing video games); and distal anthropometric outcomes of ↓ proportion of OW/O and ↓ body mass index (BMI) z-score. We anticipate an overall decrease in BMI z-score in intervention preschoolers because we expect OW/O preschoolers’ BMI z-score to decrease and healthy-weight preschoolers to have no change. We focus on proximal behavioral changes as our primary outcome instead of distal anthropometric outcomes due to the brevity of this study and the need for behavioral changes to be maintained for at least a year before manifesting in changes in anthropometric outcomes.^{49,50} **AIM 2: Examine the preliminary efficacy of *FirstStep2Health* vs control among caregivers** on their ↑ MVPA measured by accelerometry, ↑ diet quality (e.g., ↑fruits/vegetables, ↑fiber), ↓ screen time, ↓ proportion of OW/O, ↓ BMI, ↑ knowledge, ↑ feeding practice skill, ↑ self-efficacy, ↑ parental support of their child, ↑ parenting practices, and ↑ home environment. **AIM 3: Compare *FirstStep2Health* vs control on the bidirectional relationship** (as demonstrated in the APIM) between preschoolers and caregivers on MVPA, diet quality, and screen time. Further, we will **validate established feasibility, acceptability, and satisfaction of the intervention using qualitative and quantitative data**.

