
A.2. SCIENTIFIC PREMISE. The major root causes of OW/O in low-SES preschoolers and their primary caregivers include unhealthy diet (e.g., excessive sugar drinks and fat intake, increased portion size, low intakes of fruits and vegetables),^{6,73} decreased PA,⁶ increased screen time,^{74,75} poor parenting practices, and home environment.^{28-30,76} Previous interventions involving caregivers via face-to-face contact^{16,33,77} resulted in low attendance (32-38%) due to inflexible caregiver schedules.^{41,42,63} Internet-based interventions resulted in similar or even greater effects on weight loss compared to non-Internet-based interventions.⁷⁸⁻⁸⁰ However, they suffer high attrition and low usage rates.⁸¹ To address these limitations, this research uses existing social networks (i.e. Facebook)³⁹ and incorporates activities into people's daily routines.⁴⁰ According to the Pew Research Center, about 80% of young U.S. adults¹⁰ and 74% of U.S. parents¹¹ use Facebook. In our prior study, 91% of the participating young parents used Facebook. Facebook-based interventions have achieved high retention rates (77-100%).^{39,40} To date, Facebook-based interventions have focused on changing Facebook users' behaviors directly⁸²⁻⁸⁵ but no intervention has targeted caregivers via Facebook to improve support for their preschoolers' behavioral change. Some face-to-face contact is still crucial to connect caregivers to each other to initiate a communication network^{86,87} and create norms to boost participation.⁸¹ Guided by the promising findings of our prior study,³⁸ **we plan to extend this science in 3 ways:** **1)** use the existing social network Facebook™ to form a private group with messaging designed to engage caregivers in the program and to create group norms to support ongoing interaction; **2)** actively engage both preschoolers and their caregivers to target major root causes of OW/O including diet, PA, screen time, parenting practices, and home environment; and **3)** send preschooler letters to caregivers via Facebook messenger to share their preschooler's experiences of learning at school, his/her stated desires for healthy diet and PA at home, as well as ask caregivers to provide nutritious foods and types of PA the preschooler has tried and liked. Thus, we will increase caregiver engagement and retention by forming a private homogeneous virtual community on Facebook, supplemented with limited face-to-face contact to maintain participation. Our Facebook-based program has resulted in high caregiver attendance (87%).³⁸ **To our knowledge, this intervention is the first to apply a bidirectional framework that captures not only caregivers' ability to influence their preschoolers but also preschoolers' ability to influence caregivers.** A bidirectional framework emphasizing the interaction between caregivers and preschoolers offers a new perspective for studying child behaviors.^{88,89} Preschool is the time when a child's influence emerges. Erikson's psychosocial stage theory⁹⁰ indicates that children begin to assert autonomy by making choices about what they like between 18 months and 3 yrs. Children as young as 3 yrs. begin to have a significant role in influencing family food purchasing and consumption,^{91,92} so increasing children's exposure to healthy choices will help increase their requests for

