on previous literature^{10,11,132} and our prior study. To address the unique needs of this low-SES population,⁴ the program will **1)** provide caregivers a weekly electronically retrievable flyer containing health information, family fun activities, and behavioral change strategies to help create a healthier home environment, and **2)** encourage interactive positive communication to promote peer support. All program materials will be sensitive to

participants' literacy level, low-SES & use of images as confirmed in our prior work. The program has 6 components (Table 3).

Three face-to-face caregiver meetings: MSU Extension health educators will lead the meetings at Head Start centers (wks. 1, 8, & 16; **Support Letter**) to connect caregivers to each other, offer health information, and discuss behavioral change strategies. To improve attendance and accommodate caregivers' work schedules, each meeting will be held on a weekday and a weekend day at each center. Healthy food

taste-testing activities will be offered to expose caregivers to a variety of healthy homemade meals provided by MSU Extension. **Meeting 1:** A healthy, slow cooking demonstration will be offered, and each family will receive a small bag of groceries to facilitate preparation of the demonstrated recipe at home. Alternative cooking ingredients will be discussed to help reduce sugar and fat. Each caregiver will also receive an intervention cookbook containing affordable, slow-cooking recipes, quick-fix recipes, and healthy snack ideas. Reasons for providing a cookbook are: **1)** in our prior study, Head Start caregivers requested "quick fix," affordable but healthy, recipes;⁴ and **2)** using a slow cooker to prepare easy but healthy meals is an effective strategy to overcome low-SES parent barriers of lack of time and cooking skills.^{4,133} **Meeting 2:** Extension health educators will demonstrate how to spend less and shop healthy, and how to read nutrition fact labels to promote healthy purchasing behaviors. Each caregiver will receive two, durable plastic "MyPlate" adult and child meal-portion plates to guide their proper portion size. **Meeting 3:** Extension health educators will present community healthy eating and PA resources (e.g., farmer's markets, community gardens, nearby parks or

Table 2. Caregiver Weekly Habit-Formation Tasks via Facebook

Task	Instructions

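### Aim 1 counts a fall in total sugars as better diet while also seeking more fruit and dairy, which add to total sugars, so that one component can give an ambiguous result

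*Combined protocol and SAP*

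**What the plan says.** The Specific Aims, under Aim 1, name "moderate-to-vigorous PA (MVPA) measured by accelerometry (primary outcome") and then list better diet quality among the behavioral outcomes in preschoolers. The diet components are given as examples, each with an arrow for the wanted direction. After an up arrow, the list reads "fruits/vegetables, ↑ fiber, ↑ whole grains, ↑ total protein, ↑ dairy, ↓ sugar-sweetened beverages, ↓ total sugars/fats".

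Table 5, in the preschooler rows, is less specific: "Diet quality (e.g., fruit/vegetable, fiber, sugar/fat"). It does not say which sugar variable will be analysed. Intake at the center comes from observed snacks and lunch. For the rest of the day Table 5 gives "Intake at home: proxy-reported 24-hour dietary recall", and C.14 says the recalls are taken "using the Nutrition Data System for Research (NDSR) software".

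On why sugar matters, A.2 names as root causes "excessive sugar drinks and fat intake, increased portion size, low intakes of fruits and vegetables". On what caregivers are taught, C.10.1 says of Meeting 1: "Alternative cooking ingredients will be discussed to help reduce sugar and fat".

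No section mentions added or free sugars. Nor is there an energy adjustment, a diet-quality index or a rule for combining the components. C.15 analyses the Aim 1 outcomes by mixed models with group contrasts.

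**The concern.** Total sugars are the sum of added sugars and the sugars that occur naturally in food, including those in fruit and milk. One sentence of Aim 1 therefore asks for more fruit, more dairy and less of a quantity that fruit and dairy increase. The sugar that the rationale and the cooking content aim at is the sugar in drinks and recipes, and total sugars measure that only in part.

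The conflict is foreseeable from the plan's own figures. C.2 reports that the 10-week version raised preschoolers' fruit and vegetable intake (d = 0.40), and A.1 says only 9% of Head Start preschoolers meet the fruit and vegetable recommendation. A rise in fruit is thus both sought and plausible.

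What is at stake is the use of the estimate. C.6 says the purpose is to estimate effect sizes on which later research can build, and it anticipates d = 0.50 for diet quality. A total-sugars effect near zero, or in the wrong direction, could mean that added sugars did not fall. It could equally mean that they fell while fruit and milk rose. The component alone cannot separate the two.

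**Working it through.** **The plan's own figure.** The plan gives no sugar figure. The nearest number is the sample size in C.6: 130 participants, power .80, d = 0.50, significance level .05, class ICC 0.01. With a two-sided test (assumed) and 6 dyads per class, the design effect is 1 + (6 − 1) × 0.01 = 1.05. Then n per arm = 2 × (1.960 + 0.842)² / 0.50² × 1.05 = 62.8 × 1.05 = 65.9, so 66 per arm and 132 in total. At 130 the power is 0.794. The stated figure is reproduced on the plan's class-level assumption. It does not depend on how sugar is defined.

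**Which way each target moves total sugars**

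| Target in Aim 1 | Effect on total sugars | Effect on added sugars |
|---|---|---|
| More fruit | up | none |
| More dairy (as plain milk) | up | none |
| Fewer sweetened beverages | down | down |

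These directions follow from the definition of total sugars. Gram values set only the size of the conflict.

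**Illustration.** The inputs are assumptions, because the documents give none: 10, 15 or 20 g sugar per fruit serving; 12 g per cup of milk; 25 g per 8 oz sweetened drink. The daily change is F servings more fruit, half a cup more milk and half a drink less.

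- Change in total sugars = F × (10, 15, 20) + 0.5 × 12 − 0.5 × 25
- Change in added sugars = −0.5 × 25 = −12.5 g

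| F | Fruit at 10 g | Fruit at 15 g | Fruit at 20 g | Added sugars |
|---|---|---|---|---|
| 0.5 | −1.5 g | +1.0 g | +3.5 g | −12.5 g |
| 1.0 | +3.5 g | +8.5 g | +13.5 g | −12.5 g |

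**Break-even, on a second set of assumed ranges.** Take 8 to 16 g per fruit serving, 10 to 12 g per cup of milk and 2.5 to 3.3 g per fl oz of sweetened drink. Break-even cut in drinks = (sugar from extra fruit + sugar from extra milk) / sugar per fl oz.

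- Smallest case: 0.5 × 8 + 0.5 × 10 = 9 g, and 9 / 3.3 = 2.7 fl oz a day.
- Largest case: 1.5 × 16 + 1 × 12 = 36 g, and 36 / 2.5 = 14.4 fl oz a day.
- Middle case: 1 × 12 + 1 × 12 = 24 g, giving 24 / 3.3 = 7.3 to 24 / 2.5 = 9.6 fl oz a day.

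If drinks are the only source cut, a child below the break-even shows a rise in total sugars while improving on fruit, dairy and beverages. Above it, total sugars fall. A child who drinks no sweetened beverages and cuts no other added sugar can only show a rise.

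**Sensitivity to other cuts.** Suppose a further 12.5 g a day comes off other sweetened foods (assumed). The half-serving row becomes −1.5 − 12.5 = −14 g to +3.5 − 12.5 = −9 g. The full-serving row becomes +3.5 − 12.5 = −9 g to +13.5 − 12.5 = +1 g. The conflict then largely disappears from the total, although total sugars still understate the 25 g fall in added sugars.

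**The case against.** The strongest reply is that this concerns one item in a list of examples, within an outcome that is not primary, in a study meant for estimation. That is right, and it limits the point.

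A reader might infer that a child who changes as intended would be counted as a failure, or that the diet-quality outcome as a whole would be pulled the wrong way. The documents do not support this. They define no composite, score or responder rule, and the analysis compares groups. In the illustration above, the fruit, dairy and beverage components all read as improved.

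A reader might also infer that the sign of the sugar result could never be interpreted. That is too strong as well. Fruit, dairy and sweetened beverages are listed beside it, so a rise in total sugars could be read against them in the same children. The ambiguity belongs to the component and its effect size taken alone.

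The illustration also leaves things out. It credits only half a drink as reduced sugar and ignores the cooking substitutions, the snack ideas and the portion plates. It treats the whole fruit and vegetable increase as fruit and all dairy as milk; vegetables or cheese would add less. It takes the extra fruit and milk as additions to the diet rather than replacements for sweetened foods. These objections stand as to size, and they are why a misleading result is possible rather than expected.

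Finally, Table 5 does not say total sugars, so it leaves the variable open. Aim 1 does name total sugars with a direction, so the matter is more than a missing definition.

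**Conclusion.** The point holds in a limited form. Aim 1 sets a direction of success for total sugars that two of its other targets oppose, and nothing elsewhere in the plan restricts sugar to added sugars or adjusts for energy. Unless cuts in sweetened drinks and other sweetened foods are large enough to offset the extra fruit and dairy, the component can show no change or a rise while all three of those intakes improve.

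On the assumed values, an added-sugar fall of 12.5 g a day can appear as a change of −1.5 to +13.5 g in total sugars; the middle-case break-even is a cut of 7.3 to 9.6 fl oz of sweetened drink a day. The direction of the conflict is certain. Its size rests on assumed sugar contents and assumed dietary changes, and substitution or wider sugar cuts would shrink it.

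The consequence is an ambiguous effect size for one diet component as a guide to the future trial. The MVPA result, the sample size and the other diet components are unaffected. Caregiver diet is also outside the point, since Table 5 measures it with a fruit, vegetable and fiber screener.

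**What to change.** In Aim 1, replace total sugars with added sugars, in g/day or per 1,000 kcal, with the unit fixed in advance. In Table 5, specify the sugar entry as added sugars, derived from the recall and observation records already planned. Keep total sugars as a descriptive quantity only.

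The sponsor should first confirm that the recall software and the center observations allow added sugars to be separated from natural ones, because the documents do not say so. If they do not, report total sugars with no direction of success and read the result beside the fruit, dairy and beverage components.

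The cost is a wording change in two places, a matching change in the analysis program and minor extra processing. Added sugars estimated from center observations may carry some error. If separation proves feasible, no further data collection is needed; the fallback needs none either. Neither route changes the sample size.
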